4.3. Exploratory Objectives

Table AMBU.4.3. Exploratory Objectives and Endpoints

Objectives	Endpoints
Exploratory	
To summarize the change in baseline in biomarkers To evaluate the time to symptomatic response	Change from baseline in fecal calprotectin Change from baseline in C-reactive protein CCI
To evaluate the time to symptomatic remission	Time to symptomatic remission (defined as $SF = 0$, or $SF = 1$ with a ≥ 1 -point decrease from baseline, and $RB = 0$)
To summarize the change from baseline of individual MMS subscores and the composite symptomatic subscore over time in patients receiving mirikizumab	The numerical value and change from baseline in each of the following items: SF (at each visit) RB (at each visit) ES (Weeks 12 and 52) The composite clinical endpoint of the sum of the SF and RB subscores (at each visit)
CCI	CCI
CCI	CCI

Abbreviations: ES = Endoscopic subscore; MMS = Modified Mayo Score; NRS = numeric rating scale; PGIC = Patient's Global Impression of Change; PGRS = Patient's Global Rating of Severity; RB = rectal bleeding; SF = stool frequency; UC = ulcerative colitis.

5. Study Design

5.1. Summary of Study Design

Study AMBU is a multicenter, open-label study designed to evaluate the safety, pharmacokinetics (PK), pharmacodynamics (PD), and clinical response of mirikizumab in pediatric patients (ages 2 to <18 years old) and to provide data for dose confirmation for Phase 3. The study population includes pediatric patients with moderately to severely active ulcerative colitis (UC), who have an inadequate response to, loss of response to, or are intolerant to nonbiologic therapy for UC (biologic-naive), and/or those who have been exposed to at least 1 biologic and/or Janus kinase inhibitor therapy for UC (biologic/ Janus kinase inhibitor-experienced).

Patients weighing >40 kg will receive a mirikizumab induction dose of 300 mg via intravenous (IV) infusion and patients weighing ≤40 kg will receive 5 or 10 mg/kg via IV infusion at Weeks 0, 4, and 8. Patients who have met the clinical response criteria at Week 12 will receive subcutaneous (SC) maintenance doses of 200 mg (weight >40 kg), or 100 mg (weight >20 kg to ≤40 kg), or 50 mg (weight ≤20 kg) every 4 weeks from Weeks 12 to 48. Patients who have not achieved clinical response at Week 12 may receive extended induction at the next higher available dose, or will be discontinued. In cases where there is no higher dose, patients may receive extended induction dosing at the current dose. Approximately 60 patients with moderately to severely active UC will be screened to enroll approximately 30 patients.

Figure AMBU.5.1 illustrates the study design.

Figure AMBU.5.1. Illustration of study design for clinical protocol I6T-MC-AMBU.

5.2. Determination of Sample Size

Lilly plans to enroll approximately 30 patients into Study AMBU, to achieve at least 25 evaluable patients with respect to evaluating mirikizumab PK. The enrollment target includes approximately 10 patients in the >40 kg category and approximately 20 patients in the \le 40 kg category.

This sample size is considered adequate to evaluate the PK of mirikizumab treatment in pediatric patients.

5.3. Method of Assignment to Treatment

Study AMBU is open-label and patients will be assigned to mirikizumab dose groups based of

6. A Priori Statistical Methods

6.1. General Considerations

Statistical analysis of this study will be the responsibility of Eli Lilly and Company (hereafter, Lilly) or its designee. The statistical analyses will be performed using SAS® Version 9.4 or higher. The latest version of the Medical Dictionary for Regulatory Activities (MedDRA®) will be used.

Analyses and summaries from assessment of endpoints described in the protocol (described in Section 4 of this SAP and Section 4 of I6T-MC-AMBU [AMBU] protocol) are planned to be included in the clinical study report (CSR). Analyses and summaries for key safety data are also planned to be included in the CSR. Results from additional efficacy analysis predefined below and other safety analyses may also be provided in the CSR, as deemed appropriate. Any analysis or summary not included in the CSR may be available upon request.

Any change to the data analysis methods described in the protocol will require a protocol amendment ONLY if it changes a principal feature of the protocol. Any other change to the data analysis methods described in the protocol and the justification for making the change will be described in the CSR.

Additional exploratory analyses of the data may be conducted, as deemed appropriate. Some of the analyses described in this document will be incorporated into interactive display tools instead of or in addition to static displays.

The Schedule of Activities outlined in the protocol specifies the allowable windows for assessments. Assessments performed outside these windows will not be excluded from any analysis, but will be reported as a protocol deviation (see Section 6.15).

6.1.1. Analysis Populations

Patient populations are defined in Table AMBU.6.1 along with the analysis they will be used to conduct. Patients will be analyzed according to the weight/treatment dose group to which they were assigned for all populations, found in Table AMBU.6.2.

Table AMBU.6.1. Definition of Population

Population	Description
Efficacy and Health Outcomes	
Modified Intent-to-Treat (mITT) Population	All enrolled patients that received at least 1 dose of treatment, even if the patient does not receive the correct dose, or otherwise does not follow the protocol. Patients will be analyzed according to the treatment to which they were assigned. Unless otherwise noted, efficacy and health outcomes analyses will be conducted on this population.
Safetya	All patients who received at least 1 dose of the study drug. Patients will be
Salety	analyzed according to the weight/treatment dose group to which they were assigned.
Pharmacokinetics	
PK evaluable	All patients who received at least 1 dose of investigational product and have
	sufficient blood sampling to allow for PK evaluation.

Abbreviation: PK = pharmacokinetic.

Table AMBU.6.2. Weight/Treatment Dose Groups for Each Analysis Study Period and Population

Study Period	Analysis Population	Weight/Treatment Dose Groups
Induction Period	mITT; Safety	≤40 kg 5mg/kg miri IV; ≤40 kg 10mg/kg miri IV; >40 kg 300mg miri IV; All miri
Induction and Maintenance Periods	mITT; Safety	≤40 kg 5mg/kg miri IV; ≤40 kg 10mg/kg miri IV; >40 kg 300mg miri IV; All miri
Maintenance Period	mITT	≤20 kg 50mg miri SC >20 kg and ≤ 40 kg 100mg miri SC >40 kg 200 mg miri SC; ≤20 kg NR 10mg/kg miri IV & 50mg miri SC >20 kg and ≤ 40 kg NR 10mg/kg miri IV & 100mg miri SC >40 kg NR 300mg miri IV & 200 mg miri SC; All miri

Abbreviations: IV = intravenous; mITT = modified intent-to-treat; miri = mirikizumab; NR = non-responder (at Week 12); SC = subcutaneous.

The weight/treatment dose groups shown in Table AMBU.6.2 reference the specific treatment regimens to which pediatric patients are assigned at Week 0 (for the induction period) and at Week 12 (for the maintenance period) and are dependent on the participants' weight at those respective visits and their clinical response status at Week 12 for the maintenance period as

^a Safety population to include induction period and overall (combined induction and maintenance period). Any additional population or subpopulations that are of interest may also be considered for safety assessment. This is a revision to the safety population text in Section 10.2 of the protocol.

defined in the protocol. The analyses for Week 12 endpoints will be summarized by the weight/treatment dose groups indicated for the induction period. Analyses of maintenance and Week 52 endpoints will primarily be summarized by the weight/treatment dose groups indicated for the combined induction and maintenance periods. Additional summaries of some Week 52 and maintenance period endpoints will be provided for the weight/treatment groups indicated for the maintenance period. Additional details are found in Section 6.10.

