6.13. Safety Analyses

The planned analyses of safety data will be performed with an intent to maintain consistency with compound level safety standards. These standards are based on internal standards which were informed by Clinical Data Interchange Standards Consortium standards, regulatory guidance (eg, Food and Drug Administration Clinical Review Template), and cross-industry standardization efforts (eg, Pharmaceutical Users Software Exchange [PhUSE] white papers from the Standard Analyses and Code Sharing Working Group provided in the PhUSE Computational Science Deliverables Catalog [PhUSE (WWW)).

Analyses of safety data will be based on the Safety population as defined in Table AMBU.6.1. The analysis treatment periods of interest will be the Induction and the combined Induction and Maintenance period; the associated weight/treatment dose groups for each period are described

in Table AMBU.6.2. Unless otherwise stated, safety data collected during the follow-up periods for patients that do not enroll in the long-term extension Study I6T-MC-AMAZ will be listed.

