6.13.1. Extent of Exposure

Duration of exposure to study treatment will be summarized by weight/treatment dose groups for the Safety population in the combined Induction and Maintenance period. For the treatment period of interest associated with the safety analysis population, exposure will be calculated as (date of last study visit during the treatment period – date of first dose for the treatment period +1 day).

Total patient-years (PY) of exposure will be reported for each of the weight/treatment dose groups. Descriptive statistics (n, mean, SD, minimum, first quartile, median, third quartile, and maximum) will be provided for patient-weeks of exposure and the frequency of patients falling into different exposure ranges will be summarized. Exposure ranges will generally be reported in weeks using the following as a guide:

- >0, ≥4 weeks, ≥8 weeks, ≥12 weeks, ≥16 weeks, ≥24 weeks, ≥32 weeks, ≥40 weeks, ≥48 weeks
- >0 to <4 weeks, ≥ 4 weeks to <8 weeks, ≥ 8 weeks to <12 weeks, ≥ 12 weeks to <16 weeks, ..., >48 weeks

Additional exposure ranges may be considered if necessary.

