6.13.2. Adverse Events

A treatment-emergent adverse event (TEAE) is defined as an event that first occurred or worsened in severity after baseline. The MedDRA Lowest Level Term (LLT) will be used in the treatment-emergent computation. The maximum severity for each LLT during the baseline period will be used as baseline. For events with a missing severity during the baseline period, it will be treated as 'mild' in severity for determining treatment-emergence. Events with a missing severity during the postbaseline periods will be treated as 'severe' and treatment-emergence will be determined by comparing to baseline severity. For events occurring on the day of first taking study medication, the start times of the study treatment and AE will be used to determine whether the event was pre- versus post-treatment. If start time for the AE is missing, it will be assumed to have started in the postbaseline period.

Summary tables of AEs to include the following:

- overview of AEs
- summary of TEAE Preferred Terms (PTs) by decreasing frequency
- summary of TEAE PTs by decreasing frequency within System Organ Class (SOC)
- summary of TEAE PTs by maximum severity by decreasing frequency within SOC
- summary of serious adverse event (SAE) PTs by decreasing frequency
- summary of AEs leading to study discontinuation, and

• listing of SAEs.

Summary tables will include the number and percentage of patients reporting an event. For events that are gender-specific (as defined by MedDRA), the number of participants at risk will include only patients from the given gender

The baseline period and postbaseline periods will be defined as follows:

- the baseline period is the Screening period, and
- the postbaseline periods will be a) the Induction period and b) the combined Induction and Maintenance period (see Table AMBU.6.2).

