6.13.3. Deaths, Other Serious Adverse Events, and Other Notable Adverse Events

The number and percentage of patients who reported a SAE (including those resulting in death) during the safety analysis treatment periods will be summarized by weight/treatment dose group using MedDRA PT nested within SOC. Events will be ordered by decreasing frequency within SOC. A listing of SAEs will be provided.

The number and percentage of patients who permanently discontinued from study treatment due to an AE (including AEs that led to death) during each period will be summarized by weight/treatment dose group using MedDRA PT nested within SOC. Events will be ordered by decreasing frequency within SOC.

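### The SAP's combined-period AE, SAE and exposure tables report subcutaneous, rescue and escalated-dose time under the Week 0 intravenous dose, and no maintenance-period safety summary is specified

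*SAP*

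**What the plan says.** **Periods.** SAP 6.13 sets the safety periods: "The analysis treatment periods of interest will be the Induction and the combined Induction and Maintenance period". For AEs, 6.13.2 repeats this: "the postbaseline periods will be a) the Induction period and b) the combined Induction and Maintenance period". For SAEs, 6.13.3 says that counts "during the safety analysis treatment periods will be summarized by weight/treatment dose group using MedDRA PT nested within SOC". Exposure is named for the combined period alone (6.13.1): "Duration of exposure to study treatment will be summarized by weight/treatment dose groups for the Safety population in the combined Induction and Maintenance period".

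**Columns.** Table AMBU.6.2 has three rows. The Induction row and the combined row both list mITT and Safety and carry the same columns: ≤40 kg 5 mg/kg IV, ≤40 kg 10 mg/kg IV, >40 kg 300 mg IV, and all mirikizumab. The Maintenance Period row is the only one with SC-dose groups and Week 12 nonresponder (NR) groups, and it lists mITT alone. Section 6.1.1 adds: "Patients will be analyzed according to the weight/treatment dose group to which they were assigned for all populations".

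**The declared change.** Footnote a to Table AMBU.6.1 limits the Safety population to induction and overall. It goes on: "Any additional population or subpopulations that are of interest may also be considered for safety assessment", and "This is a revision to the safety population text in Section 10.2 of the protocol".

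**The protocol.** Section 10.2 defines a Maintenance Safety population that requires a maintenance dose. Section 10.3.1 and the synopsis assign maintenance-period safety analyses to it. Section 10.3.4 calls for safety summaries by dose. Section 5.1 lets 5 mg/kg nonresponders move to 10 mg/kg for 12 more weeks of IV dosing before SC dosing. Section 7.1 allows three IV rescue doses after loss of response.

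**The concern.** A column headed 5 mg/kg IV will be read as a description of what patients received when their events occurred. In the combined tables it describes only the first 12 weeks. Later events and patient-time on SC dosing, on rescue IV and, for escalated patients, on 10 mg/kg are counted in the same column.

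This matters because the protocol gives the study the purpose of establishing both induction and maintenance doses for Phase 3. The combined 52-week tables are where post-Week 12 AEs appear, and they do not show which regimen was in use. Keeping Week 0 labels protects nothing here: there is no randomization, and SAP 6.2 plans no treatment comparisons. The SAP already uses the Week 12 groups on the efficacy side: "Additional summaries of some Week 52 and maintenance period endpoints will be provided for the weight/treatment groups indicated for the maintenance period". Safety has no counterpart.

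**Working it through.** **Step 1: where post-Week 12 safety data can go.**

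| Row of Table AMBU.6.2 | Populations | Columns |
|---|---|---|
| Induction | mITT, Safety | Week 0 IV dose, all |
| Induction and Maintenance | mITT, Safety | Week 0 IV dose, all |
| Maintenance | mITT only | SC dose by weight, NR groups, all |

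An AE after Week 12 falls outside the first row, and the third row is not open to the Safety population. It can only be tabulated in the second row, under the Week 0 IV dose.

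**Step 2: who is affected.**
- All patients who reach SC dosing: their SC time is under an IV label.
- All patients given rescue: that time is also under the starting label. Protocol 7.1 gives the rescue dose only by reference to the weight cohort, so it cannot be said here whether it matches the label.
- 5 mg/kg starters who escalate: their 10 mg/kg time is labelled 5 mg/kg.
- 10 mg/kg and 300 mg starters extend at the same dose, so their extended-induction time is correctly labelled.

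**Step 3: time on each regimen.** The plan states no such figure, so none can be reproduced. Inputs: IV at Weeks 0, 4 and 8; SC every 4 weeks from Week 12 to Week 48 for responders; 12 further weeks of IV and then SC to Week 48 for nonresponders who continue; end at Week 52. Each regimen is counted from its first dose to the first dose of the next, for a completer without rescue.

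- All patients: dosing visits at Weeks 0, 4, …, 48, which is 48/4 + 1 = 13.
- Week 12 responder: 3 IV and 10 SC visits. Starting regimen 12/52 = 23%; SC (52 − 12)/52 = 40/52 = 77%.
- 5 mg/kg nonresponder who escalates: 3 visits at 5 mg/kg, 3 at 10 mg/kg and 7 SC. Time: 12/52 = 23%, 12/52 = 23% and 28/52 = 54%. All 52 weeks are labelled 5 mg/kg, and 40 of them are not on it.

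**Step 4: would the existing Maintenance groups separate the regimens?** Only in part. A completer in an NR group has 52 − 12 = 40 weeks after Week 12, of which 12/40 = 30% are IV and 28/40 = 70% are SC. The ≤40 kg NR groups also merge patients who escalated with patients on 10 mg/kg from the start.

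**Step 5: cell size.** SAP 5.2 targets about 20 patients ≤40 kg and about 10 patients >40 kg (20 + 10 = 30, matching the stated total). The Maintenance row has four ≤40 kg groups and two >40 kg groups: 20/4 = 5 and 10/2 = 5. That is an average before dropout; some cells will be smaller.

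**Step 6: listings.** In 6.13.2 and 6.13.3 the only on-treatment AE listing named is of SAEs. Section 6.13 separately lists follow-up safety data for patients who do not enter the extension study, and 6.6 lists treatment discontinuations. Neither gives non-serious on-treatment TEAEs by regimen.

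**The case against.** The strongest reply is that this is a disclosed choice. Footnote a says openly that protocol 10.2 is being revised and leaves room for further populations. Protocol 10.3.1 and SAP 6.1 both allow a change that does not touch a principal feature to be explained in the CSR. Cumulative reporting by starting group is a defensible convention in an uncontrolled study of about 30 patients. This stands as far as it goes: nothing was hidden. But the footnote commits to no maintenance analysis and gives no reason for dropping one, and protocol 10.3.1 and 10.3.4 still promise more than the SAP delivers.

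Four further points have force.
- Cells are small, so a full set of tables by Week 12 group may say little more than a listing.
- The combined tables are not silent on period. Both AE periods use Screening as baseline, so the combined count minus the Induction count for a term gives the patients whose first such event came after induction. It does not give the regimen at onset, or recurrences.
- SC dose follows Week 12 weight. In the >40 kg column it is not in doubt unless a patient changes weight class; what is missing there is the separation of IV from SC time.
- Drug from an earlier regimen may still be present after a switch, so regimen at onset does not establish cause.

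A reader might infer that the AE rate at 5 mg/kg will be biased in a known direction, or that the whole safety report is mislabelled. The documents support neither. Events and patient-time move together, so the direction is unknown. The Induction tables carry the right labels, and laboratory and vital-sign displays run by visit, so they do show post-Week 12 data. The AESI subsections and the compound level safety standards are not supplied, so nothing is claimed about them.

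**Conclusion.** The point holds for the combined-period AE, SAE and exposure tables in SAP 6.13.1 to 6.13.3. Their dose labels match the treatment in use for 12 of 52 weeks (23%) in a completing responder, and for the same share in an escalated 5 mg/kg completer. The 10 mg/kg mislabelling is confined to 5 mg/kg starters who escalate; SC and rescue time is pooled under the starting dose for everyone. As specified, no on-treatment summary of AEs, SAEs or exposure is limited to maintenance or split by regimen.

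The shares are schedule arithmetic for completers without rescue. They measure time, not bias. Column-level shares would need response and continuation rates that the documents do not give. The finding concerns the final 52-week report; the Week 4 snapshots and the Week 12 interim are little affected. It is an inexpensive improvement to reporting and leaves the primary PK analysis untouched.

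**What to change.** 1. Footnote every combined-period table: the columns are Week 0 assignments and include later extended-induction IV, rescue IV and SC dosing.
2. Add a TEAE listing that shows the starting dose and the regimen in use at onset, with patient-time by regimen. Note that drug from an earlier regimen may still be present after a switch. Given the cell sizes, this is the most useful single addition.
3. Add Safety to the Maintenance Period row of Table AMBU.6.2, and add the maintenance period to 6.13.1 to 6.13.3. Report exposure, TEAEs and SAEs at least for all mirikizumab patients, and for the Week 12-assigned groups where cell size allows.
4. State the population for item 3. Protocol 10.2 requires a maintenance dose, and under protocol 5.1 a nonresponder enters maintenance only after IV dosing ends at Week 24. The SAP's NR groups imply everyone dosed from Week 12, including patients who stop during extended induction. Choose one and reconcile SAP 6.1.1 with protocol 10.2, 10.3.1 and 10.3.4.

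The cost is SAP wording, one listing and a few tables, some with very small cells. The groups are already defined and dose times are recorded in the eCRF (protocol 7.2.1), so no new data are needed.

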10.2. Populations for Analyses

For purposes of analysis, the populations are defined in [Table AMBU.6](#).

Table AMBU.6. Population Definitions

Population	Description
Modified Intent-to-Treat (mITT) Population	All enrolled patients that took at least 1 dose of treatment, even if the patient does not receive the correct treatment, or otherwise does not follow the protocol. Patients will be analyzed according to the treatment to which they were assigned. Unless otherwise noted, efficacy and health outcomes analyses will be conducted on this population.
Induction Safety	All Induction ITT patients who received at least 1 dose of the study drug. Patients will be analyzed according to the treatment to which they were assigned. Safety analyses for the induction period will be conducted on this population.
Maintenance Safety	All Maintenance ITT patients who have received at least 1 maintenance dose. Safety analyses for the maintenance period will be conducted on this population.
PK evaluable	All patients who received at least 1 dose of investigational product and have sufficient blood sampling to allow for PK evaluation.

Abbreviations: ITT = intent-to-treat; PK = pharmacokinetic.

Additional populations will be defined in the SAP.

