10.3.4. Safety Analyses

Safety data will be summarized by dose. Safety and tolerability including but not limited to AEs, infections, injection site reactions, clinical chemistry, hematology, immunogenicity, tolerability and acceptability of SC injection volumes of CCI, and questionnaires to assess the existence and severity of depression will be assessed.

For AEs, the number of treatment-emergent adverse events (TEAEs), as well as the number and percentage of patients who reported at least 1 TEAE will be summarized using Medical Dictionary for Regulatory Activities (MedDRA) for each system organ class and preferred term.

Serious adverse events (including deaths), treatment-emergent AESIs, and AEs that lead to treatment discontinuation will also be summarized using MedDRA for each system organ class and preferred term.

For laboratory analytes and vital signs, treatment-emergent abnormal shifts to low/high will be presented.

Summary tables or listings for [CCI] will be produced as needed.

Immunization history will be recorded at baseline, and any unexpected outcomes or effects related to standard of care vaccination during the study will be summarized.

Further analyses may be performed as deemed appropriate and will be detailed in the SAP.

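### Safety is tabulated by assigned dose group, so a child given a different induction dose level has adverse events reported under a dose not received

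*SAP*

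**What the plan says.** The grouping rule is explicit and repeated.

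- SAP 6.1.1, opening paragraph: "Patients will be analyzed according to the weight/treatment dose group to which they were assigned for all populations".
- SAP Table AMBU.6.1, Safety row: patients are "analyzed according to the weight/treatment dose group to which they were assigned".
- SAP 6.1.1, text on Table AMBU.6.2: the groups "reference the specific treatment regimens to which pediatric patients are assigned at Week 0 (for the induction period) and at Week 12". The column is therefore fixed by assignment, not by what was infused.
- SAP 6.13: "Analyses of safety data will be based on the Safety population as defined in Table AMBU.6.1".
- Protocol 10.2, Table AMBU.6, Induction Safety row: "Patients will be analyzed according to the treatment to which they were assigned. Safety analyses for the induction period will be conducted on this population". The Maintenance Safety row gives no grouping rule.
- Protocol 10.3.4: "Safety data will be summarized by dose", without saying whether this means assigned or received dose.

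The mITT row of SAP Table AMBU.6.1 keeps a patient "even if the patient does not receive the correct dose, or otherwise does not follow the protocol". A mismatch between assigned and received dose is thus provided for, but only in the efficacy population.

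**The concern.** Analysis as assigned is normally justified because it preserves a randomised comparison. There is none here. Dose group follows weight and, for lighter children, the order in which cohorts open. SAP 6.2 says no treatment comparisons are planned. The safety tables exist to describe what happened at each dose level, and an assigned-dose column does that only when assigned and received doses agree.

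The use most exposed is the interim analysis in SAP 6.16.2, taken when about 15 children of 40 kg or less reach Week 12. It reports adverse events, laboratory data and events of special interest as described in SAP 6.13, and it supports the dose for that weight group in Phase 3. The columns are small, so one misfiled child is visible in the rates.

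**Working it through.** The plan states no figure on this point, so there is none to reproduce. The check has two parts.

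**1. Does any other provision move the events to the dose received?**

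- Dosing deviations are recorded in the eCRF (protocol 7.6). The data exist, but no table uses them for grouping.
- Compliance counts an infusion as given if at least 80% of the planned dose was received (SAP 6.8). There is no upper limit, so an over-infused child counts as compliant.
- Important protocol deviations are listed by patient (SAP 6.15). Their categories sit in another document, and events are not re-tabulated.
- Extra safety populations may be considered (footnote to SAP Table AMBU.6.1). This is optional and names no as-treated set.

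None of them does.

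**2. How far does one child move the rates?**

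Inputs: about 20 children of 40 kg or less (SAP 5.2). The split between 5 and 10 mg/kg is not given, so 10/10 is assumed, with 5/15 to 15/5 as the range. Assume also that one child assigned 5 mg/kg received 10 mg/kg throughout induction and is the only child with the event.

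With n5 and n10 children assigned to the two levels:
- as assigned, the columns read 1/n5 and 0/n10;
- as received, they read 0/(n5 − 1) and 1/(n10 + 1).

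| Split 5 / 10 mg/kg | Assigned: 5 mg/kg | Assigned: 10 mg/kg | Received: 5 mg/kg | Received: 10 mg/kg |
|---|---|---|---|---|
| 5 / 15 | 1/5 = 20.0% | 0/15 | 0/4 | 1/16 = 6.25% |
| 8 / 12 | 1/8 = 12.5% | 0/12 | 0/7 | 1/13 = 7.7% |
| 10 / 10 | 1/10 = 10.0% | 0/10 | 0/9 | 1/11 = 9.1% |
| 12 / 8 | 1/12 = 8.3% | 0/8 | 0/11 | 1/9 = 11.1% |
| 15 / 5 | 1/15 = 6.7% | 0/5 | 0/14 | 1/6 = 16.7% |

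At 10/10, the 95% Wilson intervals as assigned are 1.8 to 40.4% (1/10) and 0 to 27.8% (0/10). As received they are 0 to 29.9% (0/9) and 1.6 to 37.7% (1/11). They overlap widely under either rule. The effect is on which column shows the event, not on any inference.

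At the interim, suppose the 5 mg/kg cohort is ten children. Protocol 5.1 fills it before 10 mg/kg opens, so assume all ten are among the 15. That leaves 15 − 10 = 5 at 10 mg/kg. As assigned the table reads 1/10 against 0/5; as received, 0/9 against 1/6 = 16.7%.

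If the misdosed child has no event, only the denominators change. If no child is misdosed, the two rules give identical tables.

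**The case against.** The strongest reply is that this will seldom happen and would not go unnoticed. The study is open-label, the IWRS assigns product with package confirmation (protocol 7.2), and site staff give every dose (protocol 7.6). Suspected overdoses go to the medical monitor and sponsor with their adverse events recorded (protocol 9.3). Noncompliant patients are listed (protocol 10.3.2.4), as are serious adverse events (SAP 6.13.2). With about 30 children, a misdosed child can be picked out individually. The output is descriptive and the All miri column is unaffected.

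As-received grouping also has difficulties of its own. The columns combine weight class and dose, so some received doses fit no cell: 300 mg in a 38 kg child is 300/38 = 7.9 mg/kg. A rule based on the majority of the three infusions would leave a child with one wrong infusion in the assigned column.

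Most of this stands. It limits the likely frequency and rules out a crude reassignment rule. It does not give a reason for assigned grouping in the safety tables, and none of the safeguards changes what those tables show. The mITT wording is standard intention-to-treat language and should not be read as a forecast of dosing errors; neither document gives a rate.

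**Conclusion.** The point holds for the Safety population. Where received and assigned induction dose levels differ, events appear under a dose the child did not receive. On an assumed 10/10 split, one such child with an event moves about 10 percentage points between columns (about 6 to 20 over the splits tried). This depends on a child being misdosed and having an event. The likelihood is low, but the correction is cheap.

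A reader might infer three stronger conclusions that the documents do not support.

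- **That the second data snapshot would make the two dose levels look alike.** That snapshot precedes the 10 mg/kg cohort (protocol 5.1, SAP 6.16.1), so there is no second column. One of about five children is 20% of the 5 mg/kg column, but this is not a shift between levels. An over-dosed child's event kept there would make 5 mg/kg look worse, not better.
- **That the PK results are misgrouped.** The SAP sentence does say all populations. However, the PK-evaluable row has no grouping rule of its own, Table AMBU.6.2 lists groups only for mITT and Safety, and the PK analysis is in a separate plan (SAP 6.12).
- **That protocol 10.3.4 contradicts the SAP.** A summary by dose is compatible with assigned dose groups.

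The point concerns induction dosing that differs from assignment. It does not cover planned later changes of dose, and it implies nothing about which dose is right.

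**What to change.** 1. In SAP 6.1.1, limit as-assigned grouping to the mITT efficacy analyses.
2. In the Safety row of SAP Table AMBU.6.1, define the groups by the induction dose actually received, derived from the infusion eCRF already used for compliance, and keep weight class as measured.
3. List every child with any infusion whose received dose differs from the assigned level, giving the assigned level, the actual mg/kg at each infusion and the adverse events. Trigger the listing on a single infusion, in either direction.
4. Show doses that match no defined weight/dose cell in that listing and do not force them into another column. Those children still count in the All miri column. State in advance how a child with infusions at mixed levels is placed.

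The cost is one derivation rule and one listing from data already collected. The footnote to Table AMBU.6.1 already revises the protocol's safety population text, so the same footnote can record this change. Under SAP 6.1, a change that does not alter a principal feature of the protocol is described and justified in the clinical study report without an amendment.
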